9.6. Data management

Full details of the data management will be described in the Data Management Plan (DMP). The DMP is bound by the provisions of CMS. Included in the DMP are (1) description of data acquisition procedures (2) physical possession and storage of data files and (3) data sharing, electronic transmission and distribution.

9.6.1. Data collection

Data collection. Through a Data Use Agreement (DUA) with CMS, University of Maryland, Baltimore (UMB) acquires adjudicated administrative claims data for the US Medicare population. There is no data collection occurring at the UMB site. The data acquired through CMS are deemed research identifiable files, which means dates of service visits, dates of birth, and zip code information are available in the data.

Physical possession and storage of data files. All original media containing sensitive data files are kept onsite by the Pharmaceutical Research Computing (PRC) Center at UMB in an access-controlled room in a fireproof locked safe. The PRC System Administrator is responsible for the upload of data onto the secure servers, which are accessible only to study personnel. Database management at PRC is built with multiple layers of security and follows best practices for securing sensitive data.

Projects requiring special handling of backups especially at the termination of the project are stored in a specific directory on the PRC system. Files are backed-up and encrypted as a whole and saved on their own non-removable backup drive.

Data access. Only study personnel approved by the Project Officer/Principal Investigator are allowed access to the assigned secure private workspace. PRC employs the principle of least privilege, allowing only authorized access for users which are necessary to accomplish assigned tasks. Study personnel must have current Health Insurance Portability and Accountability Act (HIPAA), Collaborative Institutional Training Initiative (CITI) and security training records on file with PRC before an account or access is finalized. To increase security, external access to PRC's secure environment is blocked by a UMB campus firewall, as well as a local software-based server firewall. All study personnel access is monitored on an ongoing basis using a digital footprint.

Data inventory. The staff at PRC maintain custodianship over the data files contained on the PRC server and PRC staff maintain compliance with DUA expirations.

Data Breach. In order to comply with the Privacy Act of 1974, HIPAA, federal security requirements outlined by National Institute of Standards and Technology, and DUA-required standards, PRC has adopted measures to prevent or minimize potential system security breaches.
Data sharing, electronic transmission, and distribution. Data analysis is conducted with SAS 9.4. Users are unable to upload or download data from the PRC. Files may only be outputted to directories with write access permissions. All users must abide by the project specific DUAs when sharing or distributing data.

9.7. Data analysis

- All the statistical analyses will be done in SAS 9.4.
- All the statistical tests will be two-sided at alpha level of 0.05.
- All 95% CIs will be estimated as the point estimate ± 1.96 *standard error.

9.7.1. Hypothesis testing

9.7.1.1. Hypothesis for the SCRI analysis

Hypothesis (HA1): The incidences of new onset GBS and gout in the RZV exposed person will differ in the risk window compared to the control window, as determined by an incident rate ratio not equal to 1.

These hypotheses will be tested separately for each of the two primary HOIs using the specific risk periods provided that at least 68 cases be recorded for gout (with a total cohort size of 70 000 we will have 80% power to detect relative risk of \geq 2); and at least 20 cases recorded for GBS (with a total cohort size of 1 000 000 we will have 80% power to detect relative risk of \geq 4).

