9.5.2. Sample size considerations

SCRI design sample size estimates

For the SCRI design, the required number of events was calculated based on the method for self-controlled case series studies²⁹. The sample size estimates shown in Table 4 indicate that 1 000 000 individuals are needed to detect a relative risk of at least 4.0 for GBS and 70 000 individuals are needed to detect a relative risk of 2.0 for gout. The sample size calculation only takes into consideration the control window because the risk of GBS or gout in the control window would reflect the background risk. Due to the dose spacing and the possibility of Dose 1 control window overlapping the risk window for Dose 2, the full 42-day control window for Dose 1 may not be observed, we expect this to occur in about 50% of 2 dose vaccine recipients (based on internal GSK data from 2018-2019 regarding timing of Dose 2 receipt in the US). Hence the average length of the control window observed would be about 36 days.

Table 4SCRI design sample size estimates for GBS and gout with 80%
statistical power under a two-sided type 1 error (alpha) of 0.05

Outcome	IR	CW (days)	Scalar of Risk Window	No. of cases expected per 100 000 CWs ^a	RR	Total events needed	*No. of cases expected in CW	No. of CWs (aka vaccinations) needed/100 000 ^b	**No. vaccinations needed	***No. of vaccinated people needed
	2/100 000				3	30	8	41	4,100,000	2,050,000
GBS	2/100 000 PY	36	0.098563	0.197125	4	20	4	20	2,000,000	1,000,000
	200/100 000	0			2	68	23	140	140,000	70,000
Gout	200/100 000 PY	30	0.082136	8.706365503	2.5	40	11	67	67,000	33,500

IR: Incidence rate; RR: Relative risk; CW: Control window

^a Assuming no risk from vaccination exists in CW

^b vaccinations are synonymous with post-vaccination control windows

*Total events needed were calculated using the method described by Musonda et al 29.

** Expected vaccinations were obtained assuming the control window was truly not a period od=f increased risk

*** Approximate numbers, assuming that individuals receive 2 doses

In order to use the control window (assumed to be free of risk due to vaccination) to project the number of vaccinations needed, we scaled the background risk to the length of the control window, i.e., multiplied the respective background rate by 36/365.25 for GBS and by 30/365.25 for gout.

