We then calculated the number of cases we would need in the control window for each relative risk scenario, given the minimum total number of events needed in risk and control windows combined.

For example, for a true relative risk of 2, a total of 71 cases are needed to achieve 80% power to see an association. We would expect about 47 of the 71 cases to be in the risk window and 24 to be in the control window.

To generalize to other relative risk scenarios, the number of cases in the control window out of the total events needed is [total events needed/(RR+1)]. The expected numbers in the control window (vaccinations) needed is simply the ratio of the number of cases in the control window (i.e., the number expected on the basis of the true relative risk and the total number of events needed in risk and control windows combined) and the background rate scaled to the control window length.

Cohort design sample size estimates:

For the cohort design, the sample size was estimated using Poisson Regression in the Power Analysis and Sample Size software (NCCS Statistical Software, 2013, version 12.0.2). The analysis performed for the PMR and GCA sample size estimates was based on a 183-day risk period with a cohort ratio of 1:4 exposed to unvaccinated preventive care visit comparator.

The sample size estimates shown in Table 5 indicate that a total sample of 438 239 individuals is needed to detect a relative risk of 2.0 for PMR and a total sample of 723 362 individuals are needed to detect a relative risk of 3.0 for GCA. The study is powered for the primary outcomes of PMR and GCA.

Table 5Sample sizes with cohort design for PMR and GCA with 80%
statistical power under a two-sided type I error (alpha) of 0.05,
Cohort 1:4 ratio, and 6 months follow up

Outcome	RR	Baseline	Total Cohort	Vaccinated	Control Population,
Outcome		Response	Sample Size, N	Population, N	N
PMR	2		438,239	87,648	350,591
	2.5	0.000405	242,212	48,442	193,770
	3	0.000405	164,320	32,864	131,456
	3.5		123,991	24,799	99,192
	2		1,929,204	385,841	1,543,363
	2.5		1,066,257	213,252	853,005
GCA	3	0.000092	723,362	144,673	578,689
	3.5		545,828	109,166	436,682
	4		439,133	87,827	351,306

The estimated sample sizes for the SCRI design with vaccinees (Table 4) and the cohort design with vaccinees and the unvaccinated comparators (Table 5) needed to detect the specified relative risks (≥ 4 for GBS, ≥ 2 for gout, ≥ 2 for PMR, and ≥ 3 for GCA) with 80% power is attainable.

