9.7.9. Statistical models

Statistical models for the SCRI design

The primary, secondary and sensitivity analyses of the SCRI design will use a conditional Poisson regression model. This will estimate the incidence rates generated in risk and control windows of the same individual accounting for the within *participant* dependence using generalized estimating equations for robust variance estimation. The conditional Poisson regression model is a multinomial model, where time-fixed confounders within each stratum are controlled by conditioning on the sum of events in this stratum³¹. The general form of a conditional Poisson regression model can be written as:

n_{ik}~Poisson(λ_{ik}e_{ik})

$$\log(\lambda_{ijk}) = \phi_i + \theta_k$$

The response variable is n_{ik} , the number of events for the *i*th individual in the k (risk or control) interval. The log of the time spent in the interval (lne_{ik}) is the offset term.

In the model, λ_{ik} denotes the incidence within each interval, ϕ_i is the effect for individual i (log of baseline incidence of HOI for individual i), and β_k is the effect for risk group k³². The model generates incidence rate ratio with a 95% CI.

PROC GENMOD with the Poisson distribution, a log link function, and the EXACT statement will be employed using SAS 9.4 to perform a conditional Poisson regression model. The main model will include the dependent variable (Y) as the number of events, a binary independent variable as the interval (risk or control), and the log of person days in the interval as the offset term.

The Deviance goodness of fit test will be used to evaluate the Poisson model fit. When using PROC GENMOD to fit a Poisson regression model, the "Criteria For Assessing Goodness Of Fit" output provides the Value/DF ratio. The ratio should be close to 1 to denote a good fit of the model to the data. If the Value/DF ratio is ≥ 2 , there is overdispersion, which can result in underestimation of standard error and thus overestimate statistical significance. The "DSCALE" or "PSCALE" options in the GENMOD procedure use "deviance chi-square" and "Pearson chi-square" to make the adjustment for over-dispersion. A negative binomial link function will be used should there be overdispersion.

Temporal scan statistics

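### The case counts and sizes given for 80% power in the SCRI analyses (20 GBS, 68 gout) deliver about 73–77% under the planned exact test, and section 9.5.2 mixes equal and unequal windows

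*Combined protocol and SAP*

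**What the plan says.** Section 9.7.1.1 makes the two primary SCRI tests conditional on a minimum count: "at least 68 cases be recorded for gout" and "at least 20 cases recorded for GBS". Each count is tied to 80% power, for RR 2 at 70 000 vaccinees (gout) and RR 4 at 1 000 000 vaccinees (GBS). The Abstract (section 4), section 9.5.2 and Table 4 carry the same sizes and power.

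Section 9.5.2 says that "the required number of events was calculated based on the method for self-controlled case series studies". It takes 36 days as the average GBS control window, against a 42-day risk window, and 30 days for gout. It allots total/(RR+1) of the cases to the control window. Its worked example says that "for a true relative risk of 2, a total of 71 cases are needed" and splits them 47 and 24, whereas Table 4 gives 68 at the same relative risk.

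For the analysis, section 9.7.9 specifies conditional Poisson regression in PROC GENMOD, where "the EXACT statement will be employed using SAS 9.4". It also mentions GEE robust variance. Section 9.7 gives intervals as estimate ± 1.96 standard errors and adds: "All the statistical tests will be two-sided at alpha level of 0.05".

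**The concern.** The counts were derived with one method and will be analysed with another. With a single risk-versus-control contrast, the exact conditional analysis is a binomial test on the number of risk-window cases given the total. With 20 or 68 cases that test is coarse, so a large-sample 80% need not carry over. The counts are also the stated condition for running primary safety tests, so a reader will take 80% as what the test delivers at that point.

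Separately, a 42-day risk window and a 36-day control window cannot go with a split that assumes equal windows, and two different totals for RR 2 cannot both apply to the same design.

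**Working it through.** **Inputs.** Two-sided alpha 0.05 (9.7). Risk windows of 42 days (GBS) and 30 days (gout) (9.7.6). Control windows of 36 and 30 days, and background rates of 2 and 200 per 100 000 person-years (9.5.2, Table 4). Two doses per person (Table 4 footnote). The risk-window share of time, r, is 42/78 = 0.538 for GBS and 0.5 for gout.

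**1. Reproduce the plan's totals.** The plan does not print its formula. The signed-root likelihood-ratio version for self-controlled case series is n = (1.96 + 0.8416√B)²/A, with p = RR·r/(RR·r + 1 − r), A = 2[p·ln RR − ln(RR·r + 1 − r)] and B = (ln RR)²/A × RR·r(1 − r)/(RR·r + 1 − r)².

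| Windows | RR 2 | RR 2.5 | RR 3 | RR 4 |
|---|---|---|---|---|
| Equal | 68.1 | 40.1 | 28.8 | 19.1 |
| 42:36 | 70.5 | 41.9 | 30.2 | 20.2 |

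Table 4's gout totals (68, 40) are equal-window values. Its GBS totals (30, 20) and the text's 71 are 42:36 values. Power by this formula is 79.9% at 68 gout cases and 79.5% at 20 GBS cases, so the stated 80% reproduces.

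**2. Exact power at the stated counts.**
- GBS, 20 cases, RR 4: null share 0.538; alternative share 4 × 42/(4 × 42 + 36) = 0.824. The test rejects at 16 or more risk-window cases (two-sided p = 0.029; at 15, p = 0.090). Power is 73.0%.
- Gout, 68 cases, RR 2: null share 0.5, alternative share 0.667. The test rejects at 43 or more (p = 0.038; at 42, p = 0.068). Power is 76.9%.

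A Wald test gives 70.9% for GBS and 76.9% for gout. GEE robust variance changes nothing here: when each case falls in only one window, the robust variance of the log ratio is 1/x + 1/y, with x risk-window and y control-window cases, which is the Wald variance.

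**3. Counts that do give 80%.** Exact power moves in a sawtooth. For GBS at RR 4 it first reaches 80% at 22 cases (82.1%) and stays there from 25. For gout at RR 2 it first reaches 80% at 72 (81.0%) and stays there from 77.

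**4. Power at the stated sizes,** averaged over a Poisson case count and ignoring the minimum-count condition.
- GBS, 2 000 000 doses: mean 2 000 000 × 0.00002 × (4 × 42 + 36)/365.25 = 22.3 cases; power 76.0%.
- Gout, 140 000 doses: mean 140 000 × 0.002 × (2 × 30 + 30)/365.25 = 69.0 cases; power 76.6%.

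The stay-above counts correspond to 25 × 365.25/(0.00002 × 204) = 2.24 million doses, or about 1.1 million people, and 77 × 365.25/(0.002 × 90) = 156 000 doses, or about 78 000 people.

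**5. The split.** With unequal windows, control cases = total/(1 + RR × 42/36).
- RR 4: 20/5.667 = 3.5 (Table 4: 4).
- RR 3: 30/4.5 = 6.7 (Table 4: 8).
- 71-case example at RR 2: 71/3.333 = 21.3 control and 49.7 risk (text: 24 and 47).

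For GBS at RR 4, 3.53 control cases at 0.197125 per 100 000 control windows need about 1.79 million doses, against the 2.0 million stated.

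**The case against.** A reader might infer that the 80% is an arithmetic slip. It is not: it reproduces under the cited method, and sizing by a large-sample formula is ordinary practice. The gap comes from discreteness, and for gout it is sensitive to a single case (79.5% at 67, 76.9% at 68). That stands, but averaging over the random count does not close the gap.

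The GBS 73% depends on treating 36 days as a fixed control window. With full 42:42 windows, 20 cases give 80.4%. With an assumed mix of 75% full and 25% 18-day windows, which also averages 36 days, they give about 70%. The figure should carry that condition.

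A reader might also infer that the study is underpowered or that the window error makes the GBS size too small. Neither follows. The equal-window split errs towards more GBS doses. At 2 million eligible two-dose vaccinees (section 9.2.2 expects slightly more), GBS exact power at RR 4 is about 98%. Gout at RR 2 would yield about 4 000 000 × 0.002 × 90/365.25 = 1 971 cases. The Abstract's claim that the study will ultimately have at least 80% power at these two target risks therefore survives at that accrual. The RR 3 GBS size also stands: at 4.1 million doses the mean is 36.4 cases and averaged exact power is 81.6%.

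Finally, one might say that the 20-case condition makes the GBS test a coin toss if the vaccine is safe. The documents do not settle this. At 2 per 100 000 person-years and no effect, the chance of at least 20 cases is 27% at 4.0 million doses and 46% at 4.5 million (2.25 million people, from section 9.2.2's 4.5 million × 50%). It is over 99% at 8 million (the lower end of section 9.1's 4 to 5 million vaccinees, two doses each).

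**Conclusion.** The point holds as one about stated figures and internal consistency. At the counts in section 9.7.1.1, the planned exact test has about 73% power for GBS at RR 4 and 77% for gout at RR 2, not 80%. At the stated sizes the averages are about 76% and 77%. This rests on Table 4's background rates, two doses per person and, for GBS, a control window fixed at 36 days. The Wald alternative does not restore 80%.

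The mixing in section 9.5.2 follows from the plan's own numbers: unequal-window totals are split as if windows were equal, and RR 2 carries both 71 and 68 cases without explanation. Its effect on GBS doses is conservative. The consequence is a misstated threshold and table, not an inadequate study.

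**What to change.** In the Abstract (section 4), section 9.5.2, Table 4 and section 9.7.1.1, do one of the following:
- label 80% as asymptotic and add exact power at the stated counts and sizes (about 73–76% for GBS, 77% for gout); or
- restate the 80% figures as 25 GBS cases with about 1.1 million vaccinees and 77 gout cases with about 78 000, noting that these are the counts from which exact power stays at or above 80%, first reached at 22 and 72.

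Leave the RR 3 GBS size as it is. Use control cases = total/(1 + RR × 42/36) for GBS, and reconcile 71 with 68 at RR 2 by saying which windows each assumes.

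Optionally, consider triggering the GBS test on doses accrued rather than on cases observed, with the accrual assumptions above shown.

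The cost is a recalculated table and a few sentences. No further data are needed, and the restated sizes fit within the slightly more than 2 million eligible vaccinees expected in section 9.2.2. The quoted power or sizes become slightly less favourable.

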Individuals who qualify for Medicare due to a disability are likely not comparable to the population of adults age 65 and older within the Medicare health insurance program in many important aspects, such as medical comorbidities, illness severity, and health seeking behavior.

It will be possible to obtain sufficient sample sizes for all HOIs with a study population accrual from 2018 through 2020. Conservative estimates are that 1.5 million Medicare beneficiaries with Parts A, B, and D will receive RZV in each year from 2018 through 2020, for a total RZV exposed of 4.5 million across all three years. If 50% are enrolled in Parts A, B, and D for at least 365 days, there will be a little more than 2 million individuals exposed to RZV who meet the study criteria. It will be possible to accrue 8 million unvaccinated individuals with a preventive care visit in 2018 through 2020 to achieve a 1:4 ratio of exposed to comparators for the cohort design.

All CMS CCW Medicare claims data from January 2017 through December 2021 will be obtained for the RZV exposed and the unvaccinated comparators accrued from 2018 through 2020. Data spanning five years are needed to cover a) the 365 days prior to the HOI for the SCRI design; b) the 365 days prior to the index date for the cohort design; c) the 60- and 84-day risk and control intervals for the SCRI design; and d) the 183-day risk window for the cohort design.

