10. PROTECTION OF HUMAN SUBJECTS

Adequate protections include mandatory training in human subjects research for all study team members, including HIPAA and CITI training. The study will be reviewed and approved by the UMB Institutional Review Board. Annual study reports are required for continuing review and approval for ongoing study conduct. Any concerns during the study conduct will be reported to the Institutional Review Board as soon as it is identified.

Source files and derived data resources will be maintained in project specific directories with restricted permissions. Neither source files nor derived products may be placed on personal storage or removable media, as affirmed by the PRC data access agreement for CMS CCW Medicare data. Violations of this policy may result in criminal penalty or corrective action. Investigators and staff are required to sign the PRC data access agreement and review data security policies for the PHSR department. Policy requirements include restricted data access, secure storage and strict maintenance of privacy as required by HIPAA. To maintain confidentiality and anonymity of the *participants*, data are de-identified and cannot be linked back to the individual. As required by the CMS DUA, and this project's DMP, cells of tables will be suppressed when size less than 11.

Ethical conduct of the study

The study will be conducted in accordance with all legal and regulatory requirements. Additionally, we will adhere to commonly accepted research practices, including those described in the following guidance documents:

- The European Network of Centres for Pharmacoepidemiology and Pharmacovigilance (ENCePP) Guide on Methodological Standards in Pharmacoepidemiology. Available at: [http://www.encepp.eu/standards_and_guidances/documents/ENCePPGuideonMeth StandardsinPE_Rev7.pdf]
- International Society of Pharmacoepidemiology. Guidelines for Good Pharmacoepidemiology Practices. Pharmacoepidemiology and drug safety. 2008;17(2):200-208. doi: 10.1002/pds.1471 [published Online First: 2007/09/18] [https://www.pharmacoepi.org/resources/policies/guidelines-08027/]
- FDA Guidance for Industry: Good Pharmacovigilance Practices and Pharmacoepidemiologic Assessment [https://www.fda.gov/media/71546/download]

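### The primary GBS test requires at least 20 recorded cases, a count derived for RR 4; at the projected size, with the plan's own rate, a true null would miss it about 54% to 73% of the time

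*Combined protocol and SAP*

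**What the plan says.** Protocol section 9.7.1.1 sets the rule for the two self-controlled risk interval (SCRI) primary outcomes: "These hypotheses will be tested separately for each of the two primary HOIs using the specific risk periods provided that at least 68 cases" are recorded for gout, and "at least 20 cases recorded for GBS (with a total cohort size of 1 000 000 we will have 80% power" to detect a relative risk of 4 or more. The GBS threshold is thus paired with a power statement.

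Table 4 (section 9.5.2) is the source of the 20. It is the total number of events, risk and control windows together, needed at RR 4.

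The section does not say what happens below 20 cases. The cohort hypotheses in section 9.7.1.2 carry no such condition. Section 9.7.8 does provide a descriptive fallback, but only for the COVID-19 sensitivity analyses.

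On size, section 9.2.2 expects 4.5 million vaccinees, of whom half meet the one-year enrolment requirement: "there will be a little more than 2 million individuals exposed to RZV who meet the study criteria". Section 9.1 gives the study population as about 4 to 5 million vaccinees.

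**The concern.** A total that presupposes a fourfold risk is used as the condition for testing whether there is any risk. The total case count grows with the true relative risk, so the chance of meeting the condition depends on the answer. A harmful effect brings the test into play, while absence of effect may leave it unrun.

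GBS is a primary outcome prompted by a surveillance signal (section 7). The scenario in which a formal answer could be missing is the one in which the vaccine is safe. Small counts do not require such a rule: section 9.7.9 already plans a conditional Poisson model with exact inference, which remains valid below 20 cases.

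**Working it through.** **Inputs.** Background rate 2 per 100,000 person-years, mean control window 36 days and two doses per person (section 9.5.2 and Table 4); risk window 42 days after each dose (section 9.7.6); two-sided alpha 0.05 (section 9.7); eligible vaccinees 50% × 4.5 million = 2.25 million, with 2.0 million as a lower value (section 9.2.2).

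**Reproducing the plan's figure.** The signed-root likelihood-ratio formula for self-controlled case series, with 80% power and a risk-time share of 42/78, gives 20.2 events at RR 4 (stated: 20). Control-window cases are 20/(4+1) = 4. Cases per 100,000 control windows are 2 × 36/365.25 = 0.197. So 4/0.197125 × 100,000 = 2.03 million vaccinations, or 1.015 million people (stated: 1,000,000). The 20 is therefore the RR 4 event total.

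**Expected cases and chance of missing 20.** Expected cases = N × 2 × 0.00002 × (42 × RR + 36)/365.25. For example, N = 2.25 million at RR 1 gives 90 × 78/365.25 = 19.2. The chance of fewer than 20 is the Poisson lower tail.

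| True RR | N = 1,000,000 | N = 2.0 million | N = 2.25 million |
|---|---|---|---|
| 1 | 8.5 cases; 99.9% | 17.1; 73% | 19.2; 54% |
| 1.5 | 10.8; 99% | 21.7; 33% | 24.4; 16% |
| 2 | 13.1; 95% | 26.3; 9% | 29.6; 3% |
| 3 | 17.7; 67% | 35.5; 0.2% | 39.9; <0.1% |
| 4 | 22.3; 28% | 44.7; <0.1% | 50.3; <0.1% |

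Under no effect, an expected count of 20 needs about 2.34 million vaccinees, and an 80% chance of reaching 20 needs about 2.77 million.

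**Sensitivity at RR 1, for 2.25 and 2.0 million.** The first two rates and the Dose 2 uptake are assumptions, not figures in the documents.
- Recorded rate 3 per 100,000: 28.8 and 25.6 cases; skipped 3.5% and 11%.
- Recorded rate 4 per 100,000: 38.4 and 34.2 cases; skipped 0.4% or less.
- 80% receiving Dose 2: 17.3 and 15.4 cases; skipped 71% and 85%.
- At the 4 to 5 million of section 9.1: 34 to 43 cases; skipped 0.3% or less.

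**Power with a random case count.** Power is the sum over n of the Poisson probability of n cases times the exact binomial power at n. The null proportion is 42/78, the alternative is 42RR/(42RR + 36), and the two-sided p-value is twice the smaller tail. The condition sets power to zero for n below 20.

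| N | RR | Without condition | With condition |
|---|---|---|---|
| 1,000,000 | 4 | 76% | 58% |
| 2.0 million | 4 | 97.7% | 97.7% |
| 2.25 million | 4 | 98.8% | 98.8% |
| 2.0 million | 3 | 80% | 80% |
| 2.25 million | 3 | 86% | 86% |
| 2.0 million | 2 | 31% | 29% |

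**What a result below the threshold can show.** Ten risk-window and nine control-window cases give IRR (10/9) × (36/42) = 0.95, exact 95% CI 0.35 to 2.65. That excludes both the target of 4 and the surveillance estimate of 3.18 in section 7, yet 19 cases fail the condition.

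**The case against.** Several stronger readings are tempting, and the documents do not support them.

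*The condition undermines the study's power.* A reader might infer this from the 1,000,000 figure. That is the number needed, not the number expected. At projected enrolment, power at RR 3 to 4 is unchanged, and at RR 2 the loss is about two percentage points or less.

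*The estimate would not be reported.* Section 9.7.1.1 conditions the hypothesis test. Section 9.7.9 says without condition that the model yields an incidence rate ratio with a 95% CI, and the interval is what matters most for reassurance. Nothing bars reporting it; the plan simply does not say that it will be reported when the test is not run.

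*Cell suppression blocks reporting of counts.* Section 10 states that "cells of tables will be suppressed when size less than 11". At 2.25 million and RR 1, the risk window expects 10.3 cases (46% chance of 11 or more) and the control window 8.9. Masking is likely, not certain, and the rule covers table cells, not an IRR or CI.

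*Gout is affected too.* The rule has the same form, but 2.25 million × 2 × 0.002 × 60/365.25 gives about 1,478 expected cases against a threshold of 68.

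The strongest point on the other side is the background rate. Recorded cases come from a claims algorithm with a listed positive predictive value of 50% (Table 3). If 2 per 100,000 is a true rate, recorded cases could be about double (ignoring sensitivity), and the condition would almost always be met. The plan does not say which it is. This stands as a limit on the size of the problem.

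The threshold may also have been meant as a readiness trigger, since section 9.7.1.3 phases analyses by sample size. The text does not say so, and with accrual fixed at 2018 to 2020, waiting cannot enlarge the population.

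**Conclusion.** The point holds as a should-fix. The plan contains a rule whose chance of being met rises with the true effect, and it states no fallback for a primary objective. With the plan's own rate and two-dose assumption, and 2.0 to 2.25 million vaccinees, the GBS test is skipped about 54% to 73% of the time under no effect, about 3% to 9% at RR 2, and essentially never at RR 4.

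This rests on 2 per 100,000 being the recorded rate. A higher recorded rate shrinks the problem sharply; incomplete Dose 2 uptake enlarges it. It also rests on the eligible count in section 9.2.2. The 4 to 5 million in section 9.1 matches the count before the enrolment filter, which section 9.7.6 applies to the SCRI analysis. If that many were analysed the problem would disappear, so the two sections should be reconciled.

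Separately, the stated 80% power at 1,000,000 and RR 4 is optimistic once the case count is treated as random: about 76% without the condition and 58% with it.

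**What to change.** 1. Delete the 20-case condition for GBS in section 9.7.1.1. The gout condition can go with it for consistency, though it has no practical effect at the expected size.
2. State that the GBS incidence rate ratio, with an exact conditional 95% CI and p-value, is reported whatever the case count, with cells under 11 masked as CMS requires.
3. Restate GBS power at RR 4 with a random case count: about 76% at 1,000,000 two-dose vaccinees and about 98% at about 2 million.
4. Reconcile the vaccinee counts in sections 9.1 and 9.2.2, and say whether 2 per 100,000 person-years is a true or a claims-recorded rate.

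The cost is wording. No data or new analysis is needed, and one stated power figure becomes slightly less favourable.
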